7.3.1.3 Intraoperative Frozen Section Assessment of Surgical Margins

Frozen section evaluation of the pancreatic parenchymal and hepatic (or bile) duct margins should be performed. In the event of a positive frozen section margin at either of these loci, further resection in an effort to

achieve microscopically negative margins should be performed if possible. However, the extent of additional parenchymal resection should be left to the discretion of the operating surgeon.

The superior mesenteric arterial (SMA) margin should be evaluated on permanent section only.

7.3.1.4 Specimen Orientation for Surgical Pathology

The surgeon should ensure that the specimen is oriented for the surgical pathologist. Any segment of resected vascular structure (e.g. superior mesenteric or portal vein) should be identified and marked. Relevant margins evaluated by intraoperative frozen section (i.e. the hepatic (bile) duct, and pancreatic parenchymal) should be identified. The SMA margin (the soft tissue immediately adjacent to the SMA) should be separately inked using the principles outlined in the 8th edition AJCC staging system for exocrine pancreatic cancer. Note: The SMA margin cannot be identified accurately after the specimen has been fixed in formalin or after the specimen has been dissected for histopathologic analysis.

7.3.1.5 Aborting Surgery

The planned resection should be aborted if the operating surgeon identifies:

1. Metastatic disease in distant organs (e.g. liver). Presumed disease should be biopsied and confirmed as metastatic cancer on frozen section.
2. Localized cancer that is nonetheless, in the opinion of the operating surgeon, unsafe to resect. In such cases, the **specific reasons** for aborting the operation should be enumerated in the operative report.

7.3.1.6 Operative Note Dictation and Editing: Resection Classification

The attending surgeon should dictate the operative note. The operative report should contain:

- A section detailing the operative findings with respect to the extent of disease and the primary tumor anatomy.
- A statement as to whether or not the surgeon believes there is residual macroscopic tumor following completion of the resection.

The surgeon should integrate the operative findings with the microscopic surgical margins reported on the final pathology report in order to assign a resection classification prefix of R0, R1, or R2 (defined below). Whenever possible, this prefix should be added to the final operative note before finalizing the document. An example of the final procedure description for a patient who underwent macroscopically complete tumor removal with a positive SMA margin on permanent section final pathology is: “R1 pylorus-preserving pancreaticoduodenectomy.” The definitions for the resection classification that should be utilized in operative notes include:

- R0 – macroscopically complete tumor removal with negative microscopic surgical margins (bile duct, pancreatic parenchyma, and SMA margins)
- R1 – macroscopically complete tumor removal with any positive microscopic surgical margin (bile duct, pancreatic parenchyma, or SMA margins)
- R2 – macroscopically incomplete tumor removal with known or suspected residual gross disease

7.3.1.7 Surgical Pathology

A local pathologist experienced in the diagnosis of pancreatic adenocarcinoma should carry out pathological examination of the resected pancreatic tumor specimen. Following local review, a tissue block will be sent for central re-review. See [Section 6.2.2](#).

Three primary margins (bile duct, pancreatic neck, and SMA) should be identified and inked by the surgeon and/or pathologist. Any segment of resected vascular structure (e.g. superior mesenteric or portal vein) should be identified and marked. The SMA margin (that tissue immediately adjacent to the SMA) should be separately inked according to the procedures and recommendations of the American Joint Commission on Cancer 8th edition staging system and the College of American Pathologists guidelines for reporting of resected exocrine pancreatic cancer (2012). The tumor should be thoroughly sampled (at least one section per 1 mm of greatest tumor dimension, taken perpendicular to the inked SMA margin). The distance between the closest tumor cell and the inked SMA margin (the “SMA margin distance”) should be reported.

7.3.1.8 Frozen Section Assessment of Margins

Section assessment of bile duct and pancreatic neck margins should be performed by the local pathologist in all cases as requested by the surgeon.

7.3.1.9 Permanent Section Assessments and Final Pathology Report

The pathology report should contain all of the elements outlined in the College of American Pathologists guidelines for reporting of resected exocrine pancreatic cancer (2012). In particular, there should be specific comment on:

- Histologic diagnosis with comment on the cell of origin (pancreatic vs. bile duct vs. ampulla)
- Degree of differentiation (well, moderate, poor)
- Total number of lymph nodes examined
- Number of positive nodes
- Final margins status for the bile duct, pancreatic parenchymal, and SMA margin
- Distance (in mm) from the tumor to the inked SMA margin

- Extent of tumor infiltration (if present) of the blood vessel wall for any resected major blood vessels including the maximum histologic depth of invasion (e.g. adventitia, media).

7.3.1.10 Central Re-review of Resected Tumor Specimen

Representative slides should be sent for central re-review to standardize determination of both treatment effect score and tumor grade.

Treatment effect score will be determined using the following system:

- Treatment Effect Score I - 0% residual tumor cells in the specimen (pCR)
- Treatment Effect Score II - 1 to < 5% residual tumor cells in the specimen
- Treatment Effect Score III - \geq 5% residual tumor cells in the specimen

7.3.2 Definitions of Variations in Surgical Performance

Minor Variations

The following will be considered minor surgical variations:

- Failure to perform a frozen section of bile duct or pancreatic neck margins at the time of surgery.
- Documentation of an incomplete dissection of uncinate off of SMA.
- Documentation of a lymphadenectomy less extensive than that described above.

7.3.3 Surgical Quality Control

Sites scheduling patients for surgery should notify the study chair of their intent to operate at the time the operation is scheduled. This notification should consist of an email to the study chair with the Alliance patient ID number and date of surgery, along with contact information of the site treating surgeon and credited study PI on the OPEN form.

For all patients who undergo surgery during protocol treatment (including resection or not), the Study Chair and Surgical Co-chair will review the preoperative CT scan, the operative note, the surgical pathology report, and the adverse events associated with surgery (30 days postoperative) within 60 days of surgery. This requires that sites upload the required source documentation in a timely manner (see [Section 6.1.1](#)), and complete the AE CRF without delinquency.

Specific attention will be paid to deviations as listed above, as well as adverse events that occur in association with surgery. Operative reports and outcomes which, in the opinion of the Study Chair and Surgical Co-chair, raise potential patient safety concerns will be discussed and reviewed with the credited study PI immediately. Two operations which lead to such a discussion may lead to the site being restricted from enrolling future patients.

7.4 Imaging

7.4.1 Imaging Guidelines

CT scans are the preferred imaging modality, and the images should be collected both with and without contrast, if possible. MRI scans are allowed, and they can be used if, for example, the patient is allergic to contrast or has renal insufficiency or other medical contraindication to contrast. This study requires a baseline calculated creatinine clearance of at least 45 mL/min for eligibility. Caution should be exercised with iodine-based contrast and gadolinium contrast for patients with limited renal function. Investigators should follow standard safety guidelines and local institutional policies and discuss with the Study Chair when there is concern about the use of imaging contrast agents. Chest scans must be CT or chest X-ray. Abdominal baseline and restaging scans can include either a CT or MRI. The same method of scanning used at baseline must be used for all subsequent evaluations.

Sites are to use their optimal preoperative image acquisition protocol to optimize their ability to interpret the scans.

7.4.1.1 CT Scan

Dual phase imaging

- Slice thickness: No thicker than 3mm images (however, a set of axial images 2-3 mm for review of each phase is needed). Thinner images, if obtained, should also be submitted (in case reconstructions are needed).
- Injection rate: Faster is preferable, but whatever the injection rate, the duration of the injection should be at least 30 seconds (in order to image during the pancreatic parenchymal phase, and given an average cardiac circulation time of 13-16 seconds). Injection rates should be 3-5cc/second (unless poor IV access requires slower injection times).
- Pancreatic parenchymal phase: Imaging of the abdomen (whether the entire abdomen, or just of the pancreas) should finish approximately 45-50 seconds after contrast injection terminating below the level of the horizontal course of the duodenum.
- Portal venous phase: Imaging of the entire abdomen, to begin 55-70 seconds after the start of contrast injection, to cover the liver, and pancreas to the level of the iliac crest.
- For both phases, coronal and sagittal reconstructions (2-3 mm thick, every 2-3 mm) are encouraged, but optional.

NOTE: Separate/dedicated CTs of chest/upper abdomen must be obtained at all required time points.

7.4.1.2 Chest Scans

- Lung lesions should be excluded with CT of the chest or chest X-ray.

7.4.1.3 Pre-contrast Imaging

1. SSFSE/ HASTE T2 coronal scouts 5-8 mm thickness (with or without breath-hold, per institutional standards).
2. In-Out phase T1 breath-hold T1 GRE (4-6 mm thickness) to cover liver and pancreas.
3. Out- phase T1 GRE with or without fat sat (4-5 mm thickness) for pancreas only.
4. Respiratory Triggered FSE T2 weighted images (4-6 mm thickness for liver and pancreas).
5. 2D or 3D MRCP sequence for the pancreas as performed in your institution.

7.4.1.4 Contrast Scanning

- Sequence- 3D or 2D VIBE or SPGR/ LAVA T1 GRE (2-6 mm thickness, not > 7 mm for 2D sequence) acquired preferably in the coronal or axial plane. First acquire a non-contrast sequence for confirming the coverage and quality.
- Inject Gd-chelate MR contrast volume with weight-based dosing according to the product label @ 2cc/sec.
- Dynamic scanning using a 3D or 2D VIBE or SPGR/ LAVA T1 GRE (2-6 mm thickness) is then performed in the same plane as the pre-contrast scanning at 20/70/180 seconds delay after contrast medium injection.
- Axial and coronal T1 out-phase T1FS GRE/VIBE through the liver and pancreas (same thickness as dynamic above). If needed use two sequences to cover the anatomy.

7.4.2 Central Review of Scans

Scans should be submitted to the ICL as outlined in [Section 6.4](#). There are 2 real-time scans that are reviewed by a central radiologist, which will be the reading utilized to make decisions on the protocol. If there are any uncertainties or the participating site disagrees with the first central review result, a second review by either another central reviewer or an adjudicator will be performed. This process may take additional 24-48 hours turnaround time, and such review result will be used as the final decision for the outcome determinations.

The 1st real-time review is a determination of whether the patient has borderline resectable pancreatic cancer. If the review determines the patient is eligible, then registration procedures are followed per [Section 4.4](#).

The 2nd real-time review takes place after preoperative therapy completion, and is a determination of whether the tumor is potentially resectable.

If the patient does NOT have borderline pancreatic cancer by central review, then they are not eligible for the study and are deemed a screen failure. The expected rate of screen failures is provided in [Section 13.2](#). If they are designated by the central reviewer to have borderline pancreatic cancer, then they meet eligibility criteria as per [Section 3.2.1](#).

The 2nd real-time review takes place after preoperative therapy completion, and is a determination of whether the tumor is potentially resectable. If the 2nd central review determines that the tumor meets criteria for resection, the IROC Ohio notifies the site via email, and the reviewer enters the data into Rave. The patient should then proceed to surgery as per [Section 7.3](#).

If the review determines the patient is NOT potentially resectable, then the patient should be removed from protocol therapy, and followed as per [Section 5.0](#), post-treatment follow-up. Protocol treatment will be discontinued and further treatment is at the discretion of the treating physician. See [Section 12.0](#) for further details.

8.0 DOSE AND TREATMENT MODIFICATIONS

8.1 Ancillary Therapy, Concomitant Medications, and Supportive Care

8.1.1 Patients should not receive any other agent which would be considered treatment for the primary neoplasm or impact the primary endpoint.

8.1.2 Patients should receive full supportive care while on this study.

This includes blood product support, antibiotic treatment, and treatment of other newly diagnosed or concurrent medical conditions. All blood products and concomitant medications such as antidiarrheals, analgesics, and/or antiemetics received from the first day of study treatment administration until 30 days after the final dose will be recorded in the medical records.

8.1.3 Treatment with hormones or other chemotherapeutic agents may NOT be administered except for steroids given for adrenal failure; hormones administered for non-disease-related conditions (e.g. insulin for diabetes); and intermittent use of dexamethasone as an antiemetic in solid tumor protocols.

8.1.4 Antiemetics may be used at the discretion of the attending physician, with the exception of steroids above.

As this regimen has high emetogenic potential, it is suggested that all subjects on study should receive an aggressive prophylactic antiemetic regimen, consisting of a 5HT-3 antagonist, steroid, and NK1 antagonist.

8.1.5 Diarrhea management is per the discretion of the treating physician.

This regimen has a high incidence of severe diarrhea. For symptoms of diarrhea (and/or abdominal cramping) that occur at any time during a treatment cycle, it is suggested that patients should be instructed to take an anti-diarrheal, such as loperamide. It is recommended that the anti-diarrheal should be started at the earliest sign of: (1) a poorly formed or loose stool; (2) an increase in bowel movements by 1 to 2 episodes per day compared to baseline, or (3) an increase in stool volume or liquidity. Additional anti-diarrheal measures may be implemented at the discretion of the treating physician. Patients should also be instructed to increase fluid intake to help maintain fluid and electrolyte balance during episodes of diarrhea, and IV fluids should be considered for severe diarrhea, at the discretion of the treating physician.

8.1.6 Antibiotics

Prophylactic oral antibiotic therapy is not recommended to be given at the start of study treatment. However, antibiotics should be considered for patients who have:

(a) endobiliary stent(s) with an ANC that falls below 500 mm³ or have fever; (b) diarrhea persisting for more than 48 hours despite treatment or fever with diarrhea.

8.1.7 Anticoagulants

Due to drug interactions, treatment dose warfarin for goal INR > 1.5 is not recommended. Other anticoagulants are recommended to be used for prophylaxis and treatment.

8.1.8 Palliative radiation therapy may not be administered while a subject is on the study.

8.1.9 Alliance Policy Concerning the Use of Growth Factors

Please note that during pre-surgical FOLFIRINOX treatment, WBC growth factors are required (see [Section 7.1.1](#)). During post-surgical FOLFOX, WBC growth factors are NOT required and may be used at the discretion of the physician.

Blood products and growth factors should be utilized as clinically warranted and following institutional policies and recommendations. The use of growth factors should follow published guidelines of the American Society of Clinical Oncology Recommendations for the Use of WBC Growth Factors Update. *Journal of Clinical Oncology* 33(28): 3199-3212, 2015.

The use of erythropoiesis-stimulating agents (ESAs) is allowed at the discretion of the treating investigator. If an ESA is used, it should be within the context of the most current guidelines.

The use of prophylactic white blood cell growth factor support is required for all study subjects, beginning with the first treatment cycle and administered as per established institutional guidelines. The use of biosimilar WBC growth factor products is acceptable.

Filgrastim (G-CSF) tbo-filgrastim, and sargramostim (GM-CSF)

1. Filgrastim (G-CSF)/pegfilgrastim, tbo-filgrastim and sargramostim (GM-CSF) treatment for patients on protocols that do not specify their use is discouraged.
2. Filgrastim/pegfilgrastim, tbo-filgrastim and sargramostim may not be used:
 - a) To avoid dose reductions, delays or to allow for dose escalations specified in the protocol.
 - b) For the treatment of febrile neutropenia the use of CSFs should not be routinely instituted as an adjunct to appropriate antibiotic therapy. However, the use of CSFs may be indicated in patients who have prognostic factors that are predictive of clinical deterioration such as pneumonia, hypotension, multi-organ dysfunction (sepsis syndrome) or fungal infection, as per the ASCO guidelines. Investigators should therefore use their own discretion in using the CSFs in this setting. The use of CSF (filgrastim/pegfilgrastim or sargramostim) must be documented and reported. (e.g. on CRFs per protocol requirements)
 - c) If filgrastim/pegfilgrastim, tbo-filgrastim or sargramostim are used, they must be obtained from commercial sources.

8.1.10 CYP3A4 Inhibitors

Chronic concomitant treatment with strong inhibitors of CYP3A4 is not allowed on this trial. The following drugs are EXAMPLES of strong inhibitors of CYP3A4 and are not allowed during treatment with irinotecan.

- Indinavir
- Clarithromycin
- Ketoconazole

Because lists of these agents are constantly changing, please consult and review any drugs for their potential to inhibit CYP3A4. Examples of resources that may be utilized include the product information for the individual concomitant drug in question, medical reference texts such as the FDA website, or your local institution's pharmacist.

An information handout and wallet-size card providing information for patients and their caregivers regarding potential drug interactions have been made available in [Appendix III](#).

8.1.11 CYP3A4 Inducers

Chronic concomitant treatment with strong inducers of CYP3A4 is not allowed on this trial. The following drugs are EXAMPLES of strong inducers of CYP3A4 and are not allowed during treatment with irinotecan.

- Rifampin
- Carbamazepine

Because lists of these agents are constantly changing, please consult and review any drugs for their potential to induce CYP3A4. Examples of resources that may be utilized include the product information for the individual concomitant drug in question, medical reference texts such as the FDA website, or your local institution's pharmacist.

An information handout and wallet-size card providing information for patients and their caregivers regarding potential drug interactions have been made available in [Appendix III](#).

8.1.12 Biliary Obstruction

Biliary decompression should be performed if clinically warranted. Biliary decompression should ideally be performed during the pre-registration phase and should be accomplished endoscopically, preferably with a short metallic stent.

8.1.13 Hypersensitivity/Infusion Reactions

Treat hypersensitivity and infusion reactions as per institutional standards.

8.1.14 Cholinergic Reaction

Lacrimation, rhinorrhea, miosis, diaphoresis, hot flashes, flushing, abdominal cramping, diarrhea, or other symptoms of early cholinergic syndrome may occur during or shortly after receiving irinotecan. Atropine, 0.25-1 mg IV or SC may be used to treat these symptoms. In patients with troublesome or recurrent symptoms, prophylactic administration of atropine shortly before irinotecan therapy may be considered. Additional antidiarrheal measures may be used at the discretion of the treating physician. Combination anticholinergic medications containing

barbiturates or other agents (e.g. DonnatalR) should not be used because these may affect irinotecan metabolism. Anticholinergics should be used with caution in patients with potential contraindications (e.g. obstructive uropathy, glaucoma, tachycardia, etc.).

8.1.15 Neurologic Toxicity

Supportive care is allowed at the discretion of the treating physician. For pharyngo-laryngeal dysesthesia, it is recommended to increase the duration of oxaliplatin infusion to 6 hours for subsequent cycles.

8.1.16 Extravasation

Extravasation of oxaliplatin has been associated with necrosis. Extravasation should be treated according to institutional guidelines.

8.2 Dose Modifications

CTEP-AERS reporting may be required for some adverse events (See [Section 9.4](#)).

NOTE: PRO-CTCAE data should not be used for determining attribution, dose modifications, or reporting serious adverse events.

8.2.1 Dose Levels for Neoadjuvant mFOLFIRINOX and Adjuvant FOLFOX

General Guidelines for mFOLFIRINOX and FOLFOX:

If multiple adverse events are seen, administer dose based on greatest reduction required for any single adverse event observed. Reductions or holds for new cycles of treatment are based on treatment given in the preceding cycle and adverse events observed since the prior dose.

Dose modifications of 5FU, irinotecan, and oxaliplatin may occur independently of each other, based on the pattern of toxicity. Patients unable to tolerate one or more drugs due to toxicity will remain on treatment with the other drugs.

During FOLFOX, follow the same instructions for modifications, excluding instructions for irinotecan.

If 5-FU is omitted, leucovorin should also be omitted.

Once the dose of any drug has been reduced, the dose cannot be re-escalated.

If any drug is held for > 4 weeks, then that drug should be permanently discontinued.

There are no further dose reductions beyond those listed in the tables below for each drug. If further dose reduction is required, that drug should be discontinued.

mFOLFIRINOX Dose Levels:

Dose Level	5-FU infusion (mg/m ²)	Leucovorin (mg/m ²)	Irinotecan (mg/m ²)	Oxaliplatin (mg/m ²)
0*	2400	400	180	85
-1	1920	400	150	65
-2	1600	400	120	50
-3	1360	400	100	40

*Dose level 0 refers to the starting dose.

FOLFOX Dose Levels:

Dose Level	5-FU bolus (mg/m ²)	5-FU infusion (mg/m ²)	Leucovorin (mg/m ²)	Oxaliplatin (mg/m ²)
0*	400	2400	400	85
-1	320	1920	400	65
-2	250	1600	400	50
-3	200	1360	400	40

*Dose level 0 refers to the starting dose.

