8.2.2.2 Gastrointestinal Toxicity with Optimal Medical Management

For **grade 2 diarrhea**, delay 5FU, oxaliplatin, and irinotecan until recovery to grade ≤ 1 or baseline, then resume 5FU, oxaliplatin, and irinotecan at the same dose level.

For **grade 3 diarrhea**, delay 5FU, oxaliplatin, and irinotecan until recovery to grade ≤ 1 or baseline, then resume 5FU, and oxaliplatin at the same dose level and irinotecan at the next lower dose level.

For **grade 4 diarrhea**, delay 5FU, oxaliplatin, and irinotecan until recovery to grade ≤ 1 or baseline then resume 5FU, oxaliplatin, and irinotecan at the next lower dose level.

For **grade 3 or 4 nausea/vomiting**, delay 5FU, oxaliplatin, and irinotecan until recovery to grade ≤ 1 , then resume 5FU, oxaliplatin, and irinotecan at the next lower dose level.

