8.2.2.3 Mucositis

For **grade 3 mucositis**, delay 5FU, oxaliplatin, and irinotecan until recovery to grade ≤ 1 , then resume irinotecan and oxaliplatin at the same dose level and 5FU at the next lower dose level.

For **grade 4 mucositis**, delay 5FU, oxaliplatin, and irinotecan until recovery to grade ≤ 1 , then resume 5FU, oxaliplatin, and irinotecan at the next lower dose level.

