8.2.2.7 Other Non-hematologic Toxicities

For all other **grade 3 non-hematologic toxicities considered at least possibly related to treatment**, omit the responsible drug(s) until toxicity improves to \leq grade 1, then resume the responsible drug(s) at the next lower dose level.

For **grade 4 non-hematologic toxicities considered at least possibly related to treatment**, discontinue the responsible drug(s).

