12.1.2 Disease Progression

Remove from protocol therapy any patient with disease progression as per [Section 12.1.3](#) or recurrence after surgery (either Arm 1 or Arm 2 patients). Document details, including tumor measurements, on data forms.

After disease progression, patients should be followed for survival per the study calendar ([Section 5.0](#)).

Note: Biochemical progression (B-PROG) without the demonstration of objective progression (PD) of target or non-target lesion will not be sufficient indication to remove the patient from the study (see [Section 11.4.3](#)).

12.1.3 Removal of Patients from Protocol Therapy:

In the absence of treatment delays due to adverse events, treatment will be completed unless the patient experiences any one of the following scenarios. The specific indication should be described as:

- Metastatic disease identified on imaging studies
- For patients with RECIST PD with local progression only, the treating investigator should decide whether continuing protocol treatment is in the best interest of the patient
- The presence of locally advanced disease on pre-surgical restaging imaging studies (see [Appendix II](#) for definition of locally advanced pancreatic cancer)
- Decline in PS in the absence of radiographic evidence for disease progression if PS cannot be recovered (symptomatic deterioration)
- Metastatic disease identified intraoperatively and biopsy-proven
- Unresectable disease identified intraoperatively (e.g., locally infiltrative disease without metastases for which the surgeon does not feel resection is safe)
- R2 surgical resection
- Nontherapeutic (aborted) operation for any other reason
- Intercurrent illness that prevents further administration of treatment
- Unacceptable adverse event(s)
- Patient decides to withdraw from the study
- General or specific changes in the patient's condition that render the patient unacceptable for further treatment in the judgment of the investigator

Patient should be removed from protocol therapy, and followed as per [Section 5.0](#), post-treatment follow-up. Protocol treatment will be discontinued and further treatment is at the discretion of the treating physician.

12.1.4 Follow-up for Patients Removed from Protocol Therapy:

For patients who are removed from protocol therapy in any instance listed in [Section 12.1.3](#), follow patients per the schedule found in [Section 5.0](#) of the protocol for clinical and survival status.

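### With the irinotecan instructions removed, isolated grade 3 diarrhea on adjuvant FOLFOX brings a delay but no dose reduction, the same as grade 2

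*Combined protocol and SAP*

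**What the plan says.** Section 8.2.2 is a single rule set for mFOLFIRINOX and FOLFOX, and 8.2.1 gives the carry-over rule: "During FOLFOX, follow the same instructions for modifications, excluding instructions for irinotecan". There is no separate diarrhea rule for FOLFOX.

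For grades 2, 3 and 4 diarrhea, 8.2.2.2 holds all drugs until recovery to grade 1 or less or to baseline. Only the restart dose differs:

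- Grade 2: "then resume 5FU, oxaliplatin, and irinotecan at the same dose level".
- Grade 3: "then resume 5FU, and oxaliplatin at the same dose level and irinotecan at the next lower dose level".
- Grade 4: every drug restarts one level lower.

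The general guidelines in 8.2.1 add a rule for co-occurring events, "If multiple adverse events are seen, administer dose based on greatest reduction required for any single adverse event observed", and one for long holds, "If any drug is held for > 4 weeks, then that drug should be permanently discontinued". They also let the drugs be modified separately, and keep a patient who cannot tolerate one drug on the others. Section 12.1.3 lists unacceptable adverse events and investigator judgment among the reasons for removal from protocol therapy. Section 12.3 requires stopping when the protocol's constraints harm the patient.

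**The concern.** The grade 3 diarrhea rule was built for a regimen containing irinotecan, and it acts through that drug. Applied to a regimen without irinotecan, it loses its only reduction. A patient whose sole qualifying event is grade 3 diarrhea, despite the optimal management that 8.2.2.2 presumes, recovers and goes back to the dose that preceded it. There is no further step if the event recurs.

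The drug sections give reason to expect some response from 5-FU. Section 10.5 lists diarrhea among its common toxicities and says it can be dose-limiting. Section 10.4 warns that leucovorin may increase the gastrointestinal toxicity of 5-FU, diarrhea included. Section 10.2 describes oxaliplatin diarrhea as mild to moderate and usually brief. Supportive care under 8.1.5 and 8.1.6 treats the episode but leaves the next dose alone. At stake is avoidable re-exposure in a few patients. The decision rule and the sample size are not involved.

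**Working it through.** **Step 1. Delete irinotecan from each diarrhea rule, as 8.2.1 directs.**

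| Grade | Hold | 5-FU on restart | Oxaliplatin on restart |
|---|---|---|---|
| 2 | yes | same level | same level |
| 3 | yes | same level | same level |
| 4 | yes | one level lower | one level lower |

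Grades 2 and 3 become identical.

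**Step 2. Look for another rule that supplies a reduction.**

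- 8.2.2.7 would reduce: "then resume the responsible drug(s) at the next lower dose level". It covers only grade 3 non-hematologic toxicities not dealt with elsewhere, and diarrhea has its own rule.
- The greatest-reduction rule in 8.2.1 needs a second qualifying event.
- The four-week hold, drug-level intolerance (8.2.1), 12.1.3 and 12.3 stop a drug or protocol therapy. None lowers a dose by one level.
- 8.2.1 allows the drugs to be modified separately, but the specific diarrhea rule still fixes 5-FU and oxaliplatin at the same level.

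**Step 3. Compare the grade 3 rules in 8.2.2 for treatment-related toxicity, as they act on FOLFOX.**

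| Grade 3 event | Effect on FOLFOX drugs |
|---|---|
| Neutrophils | oxaliplatin lowered |
| Platelets | both lowered |
| Diarrhea | none lowered |
| Nausea/vomiting | both lowered |
| Mucositis | 5-FU lowered |
| Neuropathy | oxaliplatin stopped |
| Bilirubin | both lowered |
| ALT/AST | both lowered |
| All other non-hematologic | responsible drug lowered |

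Eight of nine lower or stop a FOLFOX drug. The creatinine rule is left out because it covers only events not attributed to treatment.

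**Step 4. Size per cycle.** Total 5-FU is bolus plus infusion, from the FOLFOX dose-level table in 8.2.1 (mg/m²):

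- Level 0: 400 + 2,400 = 2,800
- Level -1: 320 + 1,920 = 2,240
- Level -2: 250 + 1,600 = 1,850
- Level -3: 200 + 1,360 = 1,560

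Same level against one level lower: 2,800/2,240 = 1.25; 2,240/1,850 = 1.21; 1,850/1,560 = 1.19. The written rule therefore gives 25%, 21% or 19% more 5-FU than a one-level step.

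**Step 5. Number of patients.** Section 13.2 expects 40% to leave protocol treatment before surgery. Its own figure reproduces: 0.60 × 134 = 80.4, stated as 80. Section 7.0 says Arm 2 treatment ceased on 08/13/2018, so an amendment reaches Arm 1 only:

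- Evaluable: 0.60 × 62 = 37.2
- Accrued: 0.60 × (62 + 5) = 0.60 × 67 = 40.2

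These are upper limits under the planned 40%, since not everyone operated on need start FOLFOX. The documents give no grade 3 diarrhea rate on FOLFOX, so 5% to 15% is assumed. FOLFOX runs for four cycles (7.1.2), and an event after the fourth has no next dose. If first events are spread evenly over cycles (assumed), three quarters count:

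- 37.2 × 0.05 × 0.75 = 1.4; 37.2 × 0.15 × 0.75 = 4.2
- 40.2 × 0.05 × 0.75 = 1.5; 40.2 × 0.15 × 0.75 = 4.5

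That is roughly 1 to 5 patients, for at most 4 - 1 = 3 cycles each. Patients with a concurrent event that already forces a reduction are not subtracted, so the true number would be somewhat lower.

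**The case against.** The best defense is that the rule may be deliberate. Section 8.2.1 addresses FOLFOX expressly, the diarrhea rule is aimed at irinotecan (10.3 points to its boxed warning on severe diarrhea), and FOLFOX already omits that drug. Other rules also act only through irinotecan or spare 5-FU: the grade 2 bilirubin rule leaves nothing to do on FOLFOX, and grade 3 neutrophils leave 5-FU unchanged. This stands so far as intent goes: a reader might infer a proven drafting error, and nothing in the documents shows one. It does not justify the result. Once irinotecan is out of the regimen it cannot be the drug to lower, and the protocol gives no reason for treating grade 3 like grade 2.

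A reader might also infer that patients are locked into the full dose. They are not. The stopping routes listed in step 2 are real, though each ends a drug or protocol therapy and none reduces a dose.

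A third tempting inference is that the 5-FU bolus, present in FOLFOX and absent from mFOLFIRINOX, is the cause for worry. Section 10.5 does not support this. It links bolus dosing to myelosuppression and says gastrointestinal toxicity (naming anorexia, nausea and vomiting) is generally worse with continuous infusion. Its remark that diarrhea may be dose-limiting sits in nursing advice to treat symptoms and is not a dosing instruction.

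Finally, lowering 5-FU alone is a clinical preference: grade 3 nausea/vomiting, in the same subsection, lowers both drugs. That is fair, and no data in the documents decide between the two.

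**Conclusion.** The point holds as a statement of what the written rules produce: isolated grade 3 diarrhea on FOLFOX leads to a delay and then the same 5-FU and oxaliplatin doses, and reduction for diarrhea starts only at grade 4. It is a modest patient-safety improvement, with medium confidence, because the intent is not documented. The case rests on 5-FU being the remaining drug for which the protocol calls diarrhea possibly dose-limiting, and on leucovorin potentiating it.

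The estimate of roughly 1 to 5 patients depends on the planned 40% pre-surgical attrition, the assumed 5% to 15% event rate and the assumed even spread over cycles. Applying the event rate to everyone who starts FOLFOX would overstate the number, because it counts last-cycle events that have no next dose. A reader might also infer a threat to the 18-month survival result. With so few patients and at most three affected cycles each, the documents give no basis for that.

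**What to change.** Add to 8.2.2.2: *For grade 3 diarrhea during FOLFOX, delay 5-FU and oxaliplatin until grade 1 or less or baseline, then resume 5-FU (bolus and infusion) at the next lower dose level and oxaliplatin at the same dose level.*

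This follows the existing grade 3 mucositis rule in 8.2.2.3, "then resume irinotecan and oxaliplatin at the same dose level and 5FU at the next lower dose level", and restores three distinct steps: grade 2 delay only, grade 3 lower 5-FU, grade 4 lower both. If the present outcome is intended, a sentence giving the reason would do instead.

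The cost is one sentence in an amendment and a memo to sites, with no new data, patients or change to the analysis. The clinical downside is lower adjuvant 5-FU intensity in the few patients affected: 1 - 2,240/2,800 = 20% less per cycle from level 0, with no re-escalation allowed under 8.2.1. For a patient already at level -3, 5-FU would stop and leucovorin with it, leaving oxaliplatin alone.
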